Study Population	
Acute Pain  Randomized Population  Approximately 1730* participants with planned/elective surgery who are anticipated to start a paincontrol medication with existing CPIC guidelines after their surgery
 
Analytical Population  Approximately 304 participants from the randomized population who have an actionable phenotype defined as CYP2D6 IM or PM (i.e. CYP2D6 activity score <math>\leq 0.75</math>)
 
Chronic Pain  Randomized Population  Approximately 985* participants see in primary care or pain specialty clinics who are already prescribed or anticipated to be prescribed tramadol, codeine, or hydrocodone for pain control.
 
Analytical Population  Approximately 268 participants from the randomized population who have an actionable phenotype defined as CYP2D6 IM or PM (i.e. CYP2D6 activity score <math>\leq 0.75</math>)
 
Depression  Randomized Population  Approximately 1540* participants seen in primary care or psychiatry clinics who are already prescribed or anticipate to be prescribed an SSRI with existing CPIC guidelines
 
Analytical Population  Approximately 542 participants from the randomized population who have an actionable phenotype, defined as a CYP2D6 PM or ultra-rapid metabolizer (UM), or a CYP2C19 PM, rapid metabolizer (RM), or UM

	*Subject to change based on the actionable phenotype rates and missing data.
Number of Sites	11 sites with approximately 60-80 clinics
Duration of Subject Participation:	Up to one year from consent to end of follow-up

Description of implementation of intervention (e.g.,	The intervention for ADOPT PGx is the immediate return of PGx testing results to the participant's healthcare provider.

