## **10. STATISTICAL ANALYSIS PLAN AND SAMPLE SIZE**

### **10.1 Sample Size Determination**

All trials power analyses are based on a modified intent to treat analysis, comparing the subset of intervention participants with have an actionable phenotype to the subset of control participants with an actionable phenotype. Effect sizes used to estimate power are based on prior studies of pain and depression pharmacogenetic testing and described below for each trial and shown in Table 8. Several steps were taken to generate a conservative sample size estimate. First, the power requirement was set to 90%. Second, sample sizes are adjusted for a 10% drop-out (for which UF has data from several studies that this is a good estimate). Third, slightly smaller effect sizes than what was observed in prior studies was used. Finally, sample size calculations are based on an alpha of 0.049, to allow one interim analysis with an alpha of 0.001 in each study.

Due to the study design and the delay in the control arm to obtaining the genotyping results required determine the actionable phenotype subgroup assignment, it is not feasible to directly monitor the number of randomized participants in the actionable subgroup for the enrollment stopping rule. Alternatively, the observed trial specific actionable phenotype percentages and the corresponding trial specific total enrollment targets will be used to identify when enrollment can conclude for a fully powered mITT study.

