#### Acute Pain

In the University of Florida's pilot acute pain study, the difference between study arms in SIA score was -38.55 with a SD of 93.5, for a standardized effect size of 0.412. Assuming a reduced standardized effect size of 0.375, 304 participants with an actionable phenotype per group, 152 from the intervention arm and 152 from control arm, are required to achieve 90% power for a two-sided two-sample t-test. Preliminary data from the University of Florida's acute pain study indicates the proportion of participants with an actionable phenotype, genotypic or pheno-converted CYP2D6 IM or PM, will be approximately 18%. After adjusting for the subset anticipated to have an actionable phenotype, 845 participants completing all assessments, per group, are required to achieve 90% power in the sub-group analysis (1678 total). Assuming 10% drop out or lost to follow-up and 7% of participants not going on to surgery, a total of 2020 randomized participants is required to sufficiently power this study. Factoring in variability in the proportion that are IMs or PMs (15% to 24%), 1516 to 2424 randomized subjects would be need to achieve 90% power in the mITT analysis.

Chronic Pain: In the University of Florida's prior chronic pain study, the difference between study arms in composite pain score was 0.6 with a SD of 1.4, for a standardized effect size of 0.43. The same effect size was observed when assessing 3-month changes in pain scores. Assuming a standardized effect size of 0.40, 268 participants within the specified subgroup, 134 from the intervention arm and 134 from control arm, are required to achieve 90% power for a two-sided two-sample t-test. Preliminary data indicate the proportion of participants with an actionable phenotype will be 30-35%; 10-15% of participants with an actionable genotype-based phenotype (CYP2D6 IM or PM) and an additional 20% with a pheno-converted PM/IM based on drug-drug-gene interactions. After adjusting for the subset anticipated to have an actionable phenotype, 447 participants completing all assessments, per group, are required to achieve 90% power in the sub-group analysis (894 total). Assuming 10% drop out or lost to follow-up, a total of 994 randomized participants is required to sufficiently power this study. Factoring in variability of the proportion of randomized population that are IMs or PMs (24-33%), 906 to 1244 randomized subjects would be need to achieve 90% power in the mITT analysis.

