**Table 9. Sample size calculations**

Sample size calculations for each trial, assuming an alpha of 0.049 to allow for one interim analysis

Study	Assumed Actionable Phenotype	Total N	Completed N (90% assumed)	Intervention	Usual Care	Intervention: Actionable Phenotype	Usual Care: Actionable Phenotype	Effect Size	Power
Acute Pain (CYP2D6 IM/PM)	18% (15%-24%)	2,020 (2424-1516)	1,690* (2028 - 1268)	845 (1014 - 634)	845 (1014 - 634)	152	152	0.375	90.00%
Chronic Pain (CYP2D6)	30% (24% - 33%)	994 (906 - 1244)	894 (814-1118)	447 (407-559)	447 (407-559)	134	134	0.4	90.00%
IM/PM)									
Depression (CYP2D6 or CYP2C19 PM/UM)	40% (up to 60%)	1,508 (1006)	1,356 (904)	678 (452)	678 (452)	271	271	0.28	90.00%
Total		4,522	3,940	1,970	1,970	557	557		

\*Accounts for an additional 7% of participants not completing surgery

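### Acute pain: the synopsis total of about 1,730 randomised is not reconciled with the 2,020 base case in section 10.1 and Table 9, and the actionable rate behind 1,730 is not stated

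*Combined protocol and SAP*

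**What the plan says.** The synopsis (section 1, Study Population, Acute Pain) gives the randomised population as "Approximately 1730* participants with planned/elective surgery" and the analytical population as "Approximately 304 participants from the randomized population who have an actionable phenotype". The asterisk leads to a footnote saying that the totals may change with the actionable phenotype rates and missing data.

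Section 10.1 (Acute Pain) starts from the same 304, split as 152 per arm. It applies an actionable rate of about 18%, then 10% drop-out and 7% not going on to surgery, and concludes that "a total of 2020 randomized participants is required to sufficiently power this study". It adds a range of 1,516 to 2,424 randomised for actionable rates between 24% and 15%. Table 9 repeats the base case and the range in one cell, "2,020 (2424-1516", against an assumed rate of 18%.

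The general part of section 10.1 explains that the number of actionable participants cannot be monitored directly, because control-arm genotypes arrive late. The observed actionable percentage and the total enrolment target that corresponds to it are used instead to decide when enrolment can end.

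The amendment log records, under the same date (8/30/23), that enrolment numbers were updated in the synopsis and in section 10.1 and Table 9.

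**The concern.** Two randomised totals, 290 apart, are attached to the same analysable number, and only one of them comes with its assumptions. The reader can rebuild 2,020 from section 10.1 but cannot rebuild 1,730 from anything printed.

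This matters more here than in most trials. Because the analysable count is not visible during enrolment, the pairing of an actionable rate with a total is the working rule for stopping recruitment. If the synopsis total is read without its rate, a site, the DSMB or a later reader cannot tell whether stopping at 1,730 gives the primary analysis the intended 90% power or something lower.

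**Working it through.** **Inputs.** All come from section 10.1 (Acute Pain and the general text) unless noted.
- Test and power: the 152 per arm "are required to achieve 90% power for a two-sided two-sample t-test".
- Alpha: "sample size calculations are based on an alpha of 0.049, to allow one interim analysis with an alpha of 0.001 in each study".
- Effect: "Assuming a reduced standardized effect size of 0.375".
- Actionable rate: 18% base case, 15% to 24% range.
- Losses: 10% drop-out and 7% without surgery. Applied in sequence, the retained fraction is 0.90 × 0.93 = 0.837, a total loss of 16.3%.
- Synopsis total: 1,730.

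**Step 1: reproduce the plan's analysable number.** The normal approximation is n per arm = 2(z₁₋α/₂ + z₀.₉₀)² / d² = 2(1.969 + 1.282)² / 0.375², about 150.2, so 151. With the noncentral t, 151 per arm gives 89.96% power and 152 gives 90.15%. The plan's 152 per arm, 304 in total, is confirmed.

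**Step 2: reproduce the plan's randomised total.**
- Completers: 304 / 0.18 = 1,689. The plan rounds up to 845 per arm, or 2 × 845 = 1,690.
- Randomised: 1,690 / 0.837 = 2,019, against 2,020 stated. Adding the losses instead (17%) gives 1,690 / 0.83 = 2,036, so sequential losses fit better.
- Range: 304 / 0.24 / 0.837 = 1,513 and 304 / 0.15 / 0.837 = 2,421, against 1,516 and 2,424 stated. The small differences are rounding.

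The base case and the range both reproduce.

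**Step 3: put 1,730 through the same chain.** Actionable completers = 1,730 × 0.837 × rate. Power is from the noncentral t with d = 0.375 and alpha 0.049.

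| Actionable rate | Actionable completers | Power at 1,730 | Total that gives 304 |
|---|---|---|---|
| 15% | 217 | 78% | 2,421 |
| 18% | 261 | 85% | 2,018 |
| 20% | 290 | 89% | 1,816 |
| 21% | 304 | 90% | 1,730 |
| 24% | 348 | 94% | 1,513 |

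At 18% the exact power is 85.2% (85.5% by the normal approximation; 85.0% if the losses are added instead). The rate at which 1,730 yields 304 is 304 / (1,730 × 0.837) = 21.0%.

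**Step 4: can fewer losses explain 1,730 at 18%?** 1,730 × 0.18 = 311, so reaching 304 allows a total loss of only 1 − 304/311.4 = 2.4%, against 16.3% planned. With no drop-out at all, the planned 7% without surgery already leaves 1,730 × 0.93 × 0.18 = 290. Lower losses alone are therefore not a credible explanation at 18%. A mixture is possible: 19% actionable with 7.5% total loss, or 20% with 12.1%, also gives 304.

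**Step 5: the other two trials.**
- Chronic pain: 985 in the synopsis against 994 in Table 9. At the base-case rate, 985 × 0.90 × 0.30 = 266 completers and 90.0% power.
- Depression: 1,540 against 1,508. At the base-case rate, 1,540 × 0.90 × 0.40 = 554 completers and 90.7% power.

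Both totals differ from Table 9, but neither difference affects power materially.

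**The case against.** A reader might infer that the trial is sized at 85% power instead of 90%, or that section 10.1 requires 2,020 and nothing less. The documents do not support either reading.

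- **The range.** The figure 2,020 is the 18% case. Section 10.1 and Table 9 both allow 1,516 to 2,424, and 1,730 is within those limits. A rate of 21% is likewise within 15% to 24%.
- **The stopping rule.** The target follows the observed actionable rate. If 18% is observed, the matching total is 2,020, so stopping at 1,730 with 18% observed is not what the rule prescribes. The 85% figure combines one scenario's total with another scenario's rate.
- **The footnote and the amendment.** The synopsis warns that its totals may move with the actionable rate and missing data, and the log says its numbers were updated. Since 1,730 matches 21.0% almost exactly, it is probably a revised target. That is an inference, because the rate is not given.
- **The analysis set.** Section 10.3 defines the population as randomised participants with an actionable phenotype, and section 10.8 imputes missing values except after death. On that count, 1,730 × 0.18 is 311, not 261.

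The first three arguments stand, and they make the shortfall conditional. They do not remove the gap: a range that contains 1,730 does not identify it as the target, and the stopping rule needs the very pairing that is missing. The fourth carries less weight. Section 10.1 sizes the trial on completers, and imputation does not restore the information lost with missing outcomes.

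**Conclusion.** The point holds as an unreconciled enrolment target of moderate severity. The synopsis total (1,730) and the base case in section 10.1 and Table 9 (2,020) differ by 290 for the same 304 analysable participants, although the log records both places as updated under the same date.

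Assuming the planned 16.3% loss, effect size 0.375 and two-sided alpha 0.049, 1,730 gives 304 participants and 90% power at about 21% actionable, and about 261 participants and 85% power at 18%. Which applies cannot be settled from the documents, so underpowering is not shown. The sample size calculation itself is sound: 152 per arm, 2,020 at 18% and the stated range all reproduce.

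**What to change.** Give one acute pain total, with its actionable rate, assumed losses and resulting power, and use the same statement in the synopsis, section 10.1 and Table 9. The options are:
- If 1,730 rests on the observed rate, enter that rate (about 21% with the planned losses) as the current planning value in section 10.1 and Table 9.
- If the planning rate is still 18%, restore 2,020 in the synopsis.
- If 1,730 is kept at 18%, state the power as about 85%.

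In the same edit, correct two slips in the acute pain paragraph of section 10.1. The completer total printed as 1678 should be 1,690 (2 × 845, as in Table 9), and 304 is described as a per-group number although it is the total of both arms. The synopsis totals for chronic pain and depression could be aligned with Table 9 at the same time.

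The cost is protocol wording only. No endpoint, test or alpha changes. Under the third option the stated power becomes less favourable.

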## 2. INTRODUCTION

### 2.1 Background, Significance, and Rationale

#### Study Rationale

Pain and depression are conditions that impact substantial proportions of the US population. Finding safe and effective drug therapies for both conditions is challenging. In the case of treatment for acute and chronic pain, the challenge is finding effective therapy while minimizing adverse effects or opioid addiction (and the ensuing consequences). For depression, there are few clinically relevant predictors of successful treatment leading to multiple trials of inadequate therapy for some patients. Both opioid and antidepressant prescriptions can be guided by pharmacogenetics (PGx) data based on existing guidelines from the Clinical Pharmacogenetics Implementation Consortium (CPIC). A pilot study conducted during IGNITE-1, in patients with chronic pain supports the potential benefit of a genotype-guided approach to pain therapy.[1] Existing studies of tailored antidepressant therapy are small and often industry-sponsored but suggest the genotype-guided approach is superior to usual care. We propose a randomized pragmatic clinical trial that enrolls patients into three PGx-guided therapy scenarios: acute post-surgical pain, chronic pain, and depression. For each scenario, participants will be randomized to genotype-guided drug therapy versus usual approaches to drug therapy selection (hereafter referred to as usual care). Changes in patient reported outcomes representing pain and depression control using standard PROMIS scales define the primary endpoints. Secondary analyses include safety endpoints, changes in overall well-being, and economic impact represented by differences in healthcare utilization and cost effectiveness.

#### Background and Significance

Acute and chronic pain represents the most prevalent and expensive public health condition in the U.S., affecting an estimated 100M Americans with annual costs to society estimated at \$635B dollars.[2, 3] This exceeds the combined costs of cancer, AIDS and heart disease.[3] Opioids have become a mainstay of treatment for chronic pain, yet analgesic responses to opioids are widely variable in both acute and chronic pain.[4, 5] Opioid prescribing rates have more than tripled since 1999, with 65 in 100 people getting an opioid prescription in 2016, and nearly 215M opioid prescriptions dispensed.[6, 7] Nearly half of all opioid prescriptions originate in primary care, and approximately 35% are from surgeons.[8]

Tramadol, codeine, hydrocodone, and oxycodone comprise the vast majority of opioids prescribed in the U.S.[9] Codeine and tramadol are dependent on bioactivation by the CYP2D6 enzyme to morphine and O-desmethyltramadol, respectively, which have 200-fold greater affinity for the  $\mu$ -opioid receptor than their parent compounds. CYP2D6 genotype has important relevance for response to codeine and tramadol. Specifically, 5-10% of individuals are poor metabolizers (PMs), with no active CYP2D6 enzyme secondary to frameshift mutations (\*3, \*6), splicing defects (\*4), or complete gene deletion (\*5). As a result, PMs are unable to generate the active metabolites of codeine and tramadol and may derive no pain relief from these drugs.[10] Another 2-11% are intermediate metabolizers (IMs), with significantly impaired enzyme activity secondary to having both a nonfunctional and a reduced function CYP2D6 allele and may derive little pain relief from codeine and tramadol. At the opposite extreme, approximately 1-2% of individuals are ultra-rapid metabolizers (UMs) with CYP2D6 gene duplication/multiplication. UMs are at increased risk for toxic concentrations of active opioid metabolites, with reports of life-threatening toxicity and death with codeine or tramadol.[11-15] Hydrocodone and oxycodone undergo similar metabolism via CYP2D6 to compounds with 10- to 40-fold higher receptor affinity, respectively, and recent data support CYP2D6 genotype as an important contributor to hydrocodone efficacy, though risk exists for both drugs in those with UM phenotypes.[1]

Guidelines support *CYP2D6* genotype-guided use of opioid analgesics, but this is rarely done in clinical practice.[10] In a single center PCT[1], *CYP2D6* genotype-guided prescribing led to improved pain control in PMs and IMs compared to a traditional pain management approach. We now propose a multi-center PCT in which we will make recommendations based on *CYP2D6* genotype and *CYP2D6* enzyme inhibitor drug interactions that can convert individuals to PM or IM phenotypes. In PM, IM and UM we will recommend avoidance of hydrocodone, tramadol and codeine, and for normal metabolizers (NM), tramadol will be recommended as the preferred opioid, given its opioid and non-opioid mechanisms and purported lower risk for misuse.[16, 17] One study suggested the potential for abuse and dependence with tramadol in patients with chronic non-cancer pain was significantly less than for hydrocodone, and not different from that of non-opioid analgesics.[16]

The prevalence of major depressive disorder ranges from 5 to 10% in primary care, and it can be as high as 37% after critical care hospitalizations and surgeries.[18] SSRI prescriptions have increased 5.8-fold between 1991 and 2011.[19] Response to SSRIs and other antidepressants depends on numerous factors, but pharmacokinetic adjustments based on drug-drug interactions, renal and hepatic function, and pharmacogenomic variants within *CYP2D6* and *CYP2C19* play a substantial role in interindividual drug response.[20]

Existing clinical trials of PGx-guided treatment of depression have been primarily industry-sponsored and often investigate proprietary treatment algorithms.[21] One open label, non-randomized study demonstrated significantly improved depression outcomes in 227 adults with major depressive disorder (MDD) treated with PGx-guided prescribing of psychotropic medications relative to unguided participants.[22] Another 12-week randomized, double-blind trial of 144 adults with MDD receiving PGx-guided prescribing reported a 2.52-fold greater chance of remission of depressive symptoms. A randomized clinical trial of 685 adults with anxiety and depression identified significantly improved outcomes relative to controls in patients diagnosed with depression or anxiety using pharmacogenetic-guided medication selection.[23] A meta-analysis of randomized controlled trials of pharmacogenetic tests and depressive symptom remission concluded that individuals receiving treatment of depression with pharmacogenetic-guided decision support tools were 1.71 (95% CI: 1.17-2.48;  $p = 0.005$ ) times more likely to achieve symptom remission relative to individuals who receive treatment as usual.[24] Another industry-sponsored, randomized, double-blind prospective trial with only 51 study subjects (26 pharmacogenetic-guided versus 25 unguided) reported a trend toward improved clinical outcomes in a 10-week trial. PGx-guided participants with depression had greater than double the likelihood of response and remission. Mean percent improvement in depressive symptoms was higher for the PGx-guided group over Treatment as Usual (TAU). PGx-guided treatment doubled the likelihood of response in patients with treatment resistant depression.[25] A more recent double-blind randomized controlled trial of 316 adults with MDD failed to report a difference in sustained response within a 12-week period. However, the PGx-guided treatment group had a higher responder rate compared to treatment as usual.[26]

While the above clinical trials suggest improved depression outcomes with use of pharmacogenomic-guided management of psychotropic medications when treating major depression in outpatient psychiatric practices, the majority of the trials were small and sponsored by industry. Importantly, a large, definitive trial with non-proprietary drug selection algorithms has not yet been published. Three of the six most commonly used SSRIs (sertraline, citalopram, and escitalopram) require functional *CYP2C19* enzyme activity for their hepatic inactivation *in vivo*, and CPIC recommends dose reduction in the setting of a *CYP2C19* poor metabolizer phenotype (to reduce probability of side effects) and alternative drug in the setting of a *CYP2C19* ultra-rapid or rapid phenotype (to reduce the probability of pharmacotherapy failure).[27] Two additional common antidepressants (fluvoxamine, paroxetine) are oxidized by *CYP2D6*, one of the most polymorphic of all human enzymes. For the present investigation,

PGx-guided antidepressant selection will follow CPIC guidelines for *CYP2D6* and *CYP2C19* phenotypes with regard to the selection or dosing of antidepressants.

## **2.2 Aims and Objectives of the Study**

Our rationale for examining a genotype-guided approach to acute and chronic pain management is based on the importance of *CYP2D6* for the bioactivation of tramadol, codeine, and hydrocodone and data from a pilot study supporting improved pain control in IM/PMs in the genotype-guided arm who are taking these drugs at baseline. Similarly, the rationale for examining a genotype-guided approach to depression medication therapy is based on the demonstrated role of *CYP2D6* in the bio inactivation and *CYP2C19* oxidation of select, commonly used SSRIs. Secondly, data from industry sponsored trials support the hypothesis of improved symptom control in a genotype-guided arm.

Acute Pain: Determine if a genotype-guided approach to acute post-surgical pain therapy leads to improved pain control compared to usual care, as defined by a decrease in the SIA score. Secondarily, we will evaluate whether this approach leads to reduced use of DEA Schedule II opioids and reduced pain intensity.

Chronic Pain: Determine if a genotype-guided approach to pain therapy in participants with at least 3 months of chronic pain leads to improved pain control compared to usual care.

Depression: Determine if genotype-guided dosing or selection of antidepressants among participants with at least 3 months of depressive symptoms who require new or revised antidepressant therapy leads to improved control of depression, compared to usual care.

